## 4.2 Statistical Analysis:

### *Sample size:*

The study will be sufficiently powered to demonstrate statistically significant differences between QoL parameters in changes from Baseline to each treatment day as measured by the WURSS-21 (primary objective). Further details on the sample size determination can be found in section 8.1.

This study can fulfill its objectives only if appropriate subjects are enrolled. All relevant medical and non-medical conditions should be taken into consideration when deciding whether a subject is suitable for this protocol. Subject eligibility to participate in the clinical study should be reviewed and documented by a delegated member of the investigator's study team before subjects are randomized in the study. The following eligibility criteria are designed to select subjects for whom participation in the study is considered appropriate.

### *Population for analysis:*

A modified intention-to-treat (mITT) analysis will be performed and will include all subjects who received at least one dose of the study product(s) and have at least one post-baseline QoL questionnaire data to support at least one of the primary endpoint assessments. Any subject who is randomized but discontinues without taking any study product will be replaced. Primary and secondary analyses will be summarized using the mITT population only. Safety population will include all subjects who receive at least one dose of study product(s). Adverse events will be summarized using the Safety population. Subgroup analysis is further defined in section [8](#).

## 4.3 Inclusion Criteria

An individual must meet all the following inclusion criteria to be eligible to be included into the study:

1. Individual provides a signed and dated electronic informed consent document indicating that the subject has been informed of and consents to all pertinent aspects of the study, before any assessment is performed and individual has reviewed and is willing to follow the product label.
2. Individual aged 18 years or older at the time of electronic consent, inclusive of all ethnicities, races and gender identities.
3. Individual reporting initiation of cough symptoms within 48 hours prior to initiation of the virtual visit.
4. Individual reporting a minimum score of 5 (moderate) for cough associated with common cold symptoms and at least one other symptom of common cold (at least mild score of 3) as per the WURSS-21 symptom domains.
5. Individual reporting at least one night's sleep has been disrupted in the previous 2 nights due to the symptoms of common cold.
6. Individual who is willing to self-treat their cough using the study treatment.
7. Individual who is in good general and mental health.
8. Individual who resides in the United States (except for Hawaii and Alaska).
9. Individual who owns a mobile device with access to stable internet connection and is willing to use their device to complete study surveys and assessments per the schedule of events.
10. Individual who has not taken any cough products containing dextromethorphan, guaifenesin, or doxylamine (e.g. Robitussin, Delsym, Vicks, Mucinex), or cough

drops/lozenges containing benzocaine or menthol (e.g. Cepacol, Halls, Ricola) or any natural cough products during the study.

#### 4.4 Exclusion Criteria

An individual who meets any of the following criteria will be excluded from the study:

1. Have a history of allergies (e.g., rash, hives, difficulty breathing, swelling of face, lips, tongue, or throat) to any medication or any kind or sensitivity to ingredients in pain, cough, cold, and flu products; including the following active ingredients found in the Research products:
  - Active Ingredients – dextromethorphan, guaifenesin, doxylamine
  - Inactive Ingredients - anhydrous citric acid, carboxymethylcellulose sodium, FD&C blue no. 1, FD&C red no. 40, glycerin, liquid glucose, menthol, natural and artificial flavors, polyethylene glycol, propylene glycol, purified water, sodium benzoate, sodium citrate, sucralose, triacetin, xanthan gum
2. Individual who is currently taking medications that may interact with the study products.
3. Individual who is pregnant, lactating, or plans to be pregnant or lactating during the course of the study (self-report).
4. Individual who has taken any cough products containing dextromethorphan, guaifenesin, or doxylamine (e.g. Robitussin, Delsym, Vicks, Mucinex), or cough drops/lozenges containing benzocaine or menthol (e.g. Cepacol, Halls, Ricola) or any natural cough products within 7 days prior to the virtual visit.
5. Have previously been diagnosed with:
  - prostate gland enlargement or difficulty urinating
  - glaucoma (excessive pressure inside your eyes)
  - asthma, chronic bronchitis, chronic cough or chronic lung disease (difficulty in breathing and cough that won't go away).
  - Pneumonia (within the last 6 months)
  - COVID-19 (within the last month)
6. Are taking medication(s) to treat - psychiatric / mental health conditions (e.g. anxiety, depression) or Parkinson's disease. Medications such as:
  - MAOI (monoamine oxidase inhibitor) [e.g. Azilect, Emsam, Marplan, Nardil] or have stopped them within the last 2 weeks per your doctor's advice.
7. Are currently taking sedatives or tranquilizers (e.g. Ambien, Xanax, Klonopin)
8. Are taking drugs for heart problems such as quinidine, amiodarone or metoprolol, antidepressants such as fluoxetine and paroxetine, or antipsychotics such as haloperidol and thioridazine.
9. Individual who is currently experiencing:
  - cough accompanied by fever, rash, or persistent headache **OR**
  - cough with too much phlegm.
10. Individual who is an employee of **CCI**, either directly involved in the conduct of the study or a member of their immediate family; or a Haleon employee directly involved in the conduct of the study or a member of their immediate family.
11. Individual who has participated in other studies (including non-medicinal studies) involving investigational product(s) within 30 days prior to study entry.
12. Individual who has previously been enrolled in this study.
13. Individual sharing the same address as another individual who has been enrolled in this study.

14. Individual who, in the opinion of the investigator or delegate, should not participate in the study, including an individual who meets any of the “stop use” criteria recommended by the label.

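### The 2-week MAOI look-back in exclusion 6 covers only stops made on a doctor's advice, so a recent unadvised stop meets none of the specific drug exclusions

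*Protocol*

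**What the plan says.** Protocol 4.4, criterion 6, is written in the present tense for people taking medication for psychiatric conditions or Parkinson's disease, with MAOIs as the named example. It then reaches back to people who took an MAOI and "or have stopped them within the last 2 weeks per your doctor's advice".

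The other drug criteria in the same list are:

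- Criterion 2: "Individual who is currently taking medications that may interact with the study products".
- Criterion 4: recent use of listed cough products, lozenges "or any natural cough products within 7 days prior to the virtual visit".
- Criterion 7: "Are currently taking sedatives or tranquilizers".
- Criterion 8: "Are taking drugs for heart problems such as quinidine, amiodarone or metoprolol", together with certain antidepressants and antipsychotics.

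Criterion 11 has another look-back, for participation in studies "involving investigational product(s) within 30 days prior to study entry". Criterion 14 is a general discretion clause: "Individual who, in the opinion of the investigator or delegate, should not participate in the study". Inclusion criterion 1 (Protocol 4.3) requires that the "individual has reviewed and is willing to follow the product label", and inclusion criterion 7 requires good general and mental health.

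On process, prior medications are self-reported (Protocol 5.3.2). Eligibility is collected by survey and confirmed at the virtual visit (5.4.3.1), where staff review prior medications (5.4.3.2). SAP 4.4.2 has prior medications from the 30 days before consent recorded in the CRF.

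**The concern.** The sponsor decided that an MAOI taken within the previous 2 weeks is a reason not to enter this study. The clause that carries out that decision adds a second condition, namely who initiated the stop, and the documents give no reason why that should matter. Time since the last dose is the same whether or not a doctor was consulted.

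What is at stake is subject protection and consistent eligibility decisions. Dextromethorphan is in the daytime product and in the nighttime product, so a subject admitted through this gap is exposed to it in either arm. The study is fully decentralized and relies on self-report. Criterion 6 is worded as if addressed to the subject. If the screening survey repeats that wording (its text is not in the documents), a person who stopped unadvised could truthfully answer no. Two reviewers looking at the same medication record could then decide differently, and enrolling the subject would not breach criterion 6 as written.

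**Working it through.** No arithmetic applies beyond comparing time windows, and the plan states no figure to reproduce. The check takes one test case and runs it through every criterion that could catch it.

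**Test case.** A subject fully stopped an MAOI 5 days before the virtual visit, without a doctor's advice, and takes nothing else on the exclusion list.

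| Criterion (Protocol 4.4) | What it covers | Time scope | Met? |
|---|---|---|---|
| 2 | Interacting medications | Current use | No, the drug has been stopped |
| 4 | Cough products and lozenges | Previous 7 days | No, an MAOI is not a cough product |
| 6, first limb | Psychiatric or Parkinson's medication, including MAOIs | Current use | No, the drug has been stopped |
| 6, second limb | MAOI stopped on a doctor's advice | Previous 2 weeks | No, the stop was not advised |
| 7 | Sedatives, tranquilizers | Current use | No |
| 8 | Heart drugs, certain antidepressants and antipsychotics | Current use | No |

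None of the five specific drug criteria (2, 4, 6, 7, 8) is met.

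**Contrast case.** Change one fact: the same drug was stopped on the same day, but on a doctor's advice. The second limb of criterion 6 now applies and the subject is excluded. The two subjects differ only in who prompted the stop.

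**Comparison with the other look-backs.** Criterion 4 (7 days) depends on use and elapsed time. Criterion 11 (30 days) depends on participation and elapsed time. Criterion 5 has two more, pneumonia within 6 months and COVID-19 within a month, which require a diagnosis as well as timing. None of them depends on a doctor's advice.

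**Other provisions.** No other part of the protocol or SAP gives an MAOI washout. What remains is:

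- Inclusion 1: willingness to follow the label. The label's MAOI text is not reproduced in the documents.
- Inclusion 7: good general and mental health.
- Exclusion 14: the opinion of the investigator or delegate.
- Protocol 4.2: relevant conditions are to be weighed, and eligibility reviewed and documented, before randomization.
- Protocol 5.4.3.2: staff review of prior medications.
- SAP 4.4.2: a 30-day prior-medication record. Since 30 days exceeds 14 days, the record spans the whole MAOI window.

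These make it likely that the recent stop is seen. None of them states that it excludes the subject.

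**The case against.** The best answer is that the literal reading is strained. The phrase is in participant-facing language and more naturally describes how a prescribed drug is usually stopped than an intention to admit people who stopped on their own. Sensible staff would probably apply the 2-week window to any stop. In addition, a person who abruptly stopped a psychiatric drug without advice raises an obvious question under inclusion 7. Protocol 4.2 tells the team to weigh all relevant conditions and document the review before randomization, and the label that the subject agrees to follow may itself bar them.

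Much of this stands. The phrase is probably a drafting slip, the safeguards are real, and the practical gap is narrower than the wording alone suggests. Criterion 6 is also not the only look-back that depends on more than elapsed time, since those in criterion 5 need a diagnosis.

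It does not remove the point. Inclusion 7, exclusion 14 and the Protocol 4.2 instruction all work by judgement, whereas criterion 6 is meant to be a fixed rule. Whether the label closes the gap cannot be checked from the documents. Probable intent is a reason to correct the text, because the written rule is what gets copied into surveys and against which deviations are judged.

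**Conclusion.** The concern holds as a minor defect in an operative safety rule. As worded, exclusion 6 does not exclude a subject who fully stopped an MAOI within the past 2 weeks without a doctor's advice, and no other specific drug exclusion does so.

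The conclusion rests on the ordinary reading in which the advice phrase qualifies the stop, and on a complete stop, since a subject still taking the drug is caught by the current-use wording. Few subjects are likely to be affected, though the documents give no rate, and the information needed to spot them should be in front of the reviewer. There is no consequence for the endpoints, the analysis or the sample size.

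**What to change.** Delete the final four words of the criterion 6 clause, so that the look-back ends at the 2-week period and covers any stop, whoever initiated it. Make the same change in any matching pre-screening or screening survey item, and have the virtual-visit eligibility check apply the window to every recent MAOI stop.

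The cost is a four-word deletion in the criterion and in any matching survey item. Sample size and analysis do not change, and the only additional people excluded are those the 2-week window appears meant to exclude already.

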## 4.5 Lifestyle Considerations

As a real-world evidence study, there will be no lifestyle considerations.

## 5 STUDY ASSESSMENTS

This section lists the procedures and assessments to be completed at each planned study time point. However, as per nature of RWE studies, if a subject fails to complete their daily questionnaire at any time point post-baseline, subjects will be permitted to continue in the study. The timing of each assessment is listed in the Table 5-1 Schedule of Activities section.

### 5.1 Schedule of Activities

The Schedule of Activities ([Table 5-1](#)) provides an overview of the subjects’ virtual visit and study assessments. The investigator may schedule additional (unplanned) virtual visits to conduct additional evaluations or assessments required to protect the well-being of the subject.

**Table 5-1 Schedule of Activities**

All assessments are completed online. Subjects will receive links via email/text to complete questionnaires per the Schedule below.

	May occur same-day a									
Counterparty Assessments	Pre-screening	Screening and Baseline (Virtual Visit) Day 0	Day 1	Day 2	Day 3	Day 4	Day 5	Day 6	Day 7	2 Days after Last Dose i
Pre-screening Survey	X									
Informed consent (self-consent)	X									
Medical/Medication history b		X								
Demographics		X								
ID Verification		X								
WURSS–21 questionnaire cf (Baseline, pre-treatment)		X								
Specific QoL Questions (Baseline, pre-treatment)		X								
Eligibility Assessment		X								
Randomization		X								

Study product shippeda		X								
Study product useeg		X	X	X	X	X	X	X	X	
WURSS–21 questionnairef (post-treatment)			X	X	X	X	X	X	X	
Specific QoL Questions (post-treatment)			X	X	X	X	X	X	X	
Product Usage eDiaryh		X	X	X	X	X	X	X	X	
End of Study Surveyi									X	
Concomitant Medication Check			X	X	X	X	X	X	X	
Adverse Event/Serious Adverse Event			X	X	X	X	X	X	X	X

QoL, quality of life; WURSS–21, Wisconsin Upper Respiratory Symptom Survey-21.

*a* Pre-screening, Screening and Baseline can occur same day if product is received by subject same-day

*b* Medical history including medication history will be self-reported by participant during the virtual visit.

*c* Participant eligibility to be confirmed through assessment of inclusion/exclusion criteria and cold symptoms of at least mild intensity reported on the Baseline WURSS-21 assessment at the time of Screening.

*d* Participant to confirm receipt of study product for study enrollment confirmation and read through detailed instructions regarding product dosing; Counterparty staff will be available to answer any queries regarding product use.

*e* Robitussin: Group 1: Subjects in Group 1 will be instructed to take up to 20 ml of Robitussin per label instructions for up to 8 days or until resolution of symptoms, whichever occurs first.

Group 2: Subjects in Group 2 will be instructed to take the following per label instructions for up to 8 days or until resolution of symptoms, whichever occurs first:

- up to 20 ml of Robitussin Maximum Strength Cough and Chest Congestion DM

- up to 20 ml of Robitussin Maximum Strength Nighttime Cough DM

*f* WURSS–21 to be completed at the time of Baseline/Screening to confirm eligibility as well as daily during treatment (from Day 1 up to Day 7).

*g* Study product (Robitussin) to be shipped only after screening/baseline assessments are completed and eligibility is confirmed; up to 8 days' worth of study product(s) will be shipped together to ensure there is no interruption in study timeline or treatment duration.

*h* Participant will complete an eDiary documenting Robitussin use each day directly through the Citrus ePRO module.

*i* Participant-reported End of Study Survey will be completed at the end of study directly through the Citrus ePRO module. Participants ending product use early will complete the survey one day after their last reported dose; participants dosing on Day 7 will complete the survey on Day 7.

*j* Participant-reported Change in Health will be recorded two days after last study product administration.

## 5.2 Pre-screening

Adult subjects reporting cough associated with common cold onset within the previous 48 hours who express interest in the study, via social media platform advertising, will be directed to complete an online pre-screening questionnaire assessing their eligibility to participate in the study. The information collected from the pre-screening questionnaire serves as the preliminary screening tool to isolate potentially eligible participants from ineligible subjects.

Subjects who successfully pass the pre-screening questionnaire are deemed potentially eligible for participation and are directed to complete an online electronic informed consent form (eICF).

### **5.2.1 Informed Consent**

The Electronic Informed Consent Form (eICF) is a tool that assists in the consenting process by using multimedia components delivered by an electronic system. The eICF process for this study will be self-completed on the subject's mobile device following successful completion of the study pre-screening questionnaire. Informed consent must be obtained before any study-specific activity is performed. Once the eICF has been signed and dated by the subject, the subject will be provided with a copy via email. An additional copy of the signed eICF will be saved as a Portable Document Format (PDF) in the virtual site file.

If, during a subject's participation in the study, the eICF undergoes any changes, each ongoing subject should receive a copy of this new information and be re-consented into the study if applicable as determined by the IRB. Each subject should be provided with a copy of the signed and dated amended consent form.

Potentially eligible subjects who successfully complete the pre-screening questionnaire and execute the eICF will receive the following information: 1) a copy of the signed eICF, 2) an email/text invitation to complete the screening and baseline questionnaires and 3) an invitation to schedule the Screening & Baseline Virtual Visit.

## **5.3 Screening & Baseline Questionnaires**

Pre-screening and Screening will most likely happen on the same day. After the informed consent is executed, subjects will receive links via email/text to complete questionnaires noted below.

### **5.3.1 Demographics**

Subjects will self-report the following demographic information: year of birth and age, sex at birth, race, and ethnicity.

#### **5.3.1.1 Smoking Status**

Subjects will self-report their current smoking status, inclusive of cigarettes, e-cigarettes, vaping, etc.

#### **5.3.2 Medical History and Prior Medication/Treatment**

Relevant medical and/or surgical history (in the previous 12 months) will be self-reported, including allergies or drug sensitivity and prior medications/treatments, including prescription and non-prescription drugs, vaccines, dietary supplements and herbal remedies, that began before obtaining informed consent will be recorded as the Medical History/Current Medical Conditions.

#### **Female subjects only:**

- Female subjects who report being pregnant or confirm plans to become pregnant during the study will be excluded.

- Given the potential impact of pregnancy on study outcomes, female subjects of child-bearing potential will be reminded to inform the investigator site immediately if pregnancy is known or suspected.

## **5.4 Virtual Visit**

The Virtual Visit may occur on the same day that the subject completes the Pre-screening.

### **5.4.1 Verification of Identity**

During the virtual visit, a trained member of the study team will verify the subject's government-issued identification (i.e. photo ID such as driver's license or government issued passport) on camera at the beginning of the visit. Should the subject elect not to show a form of photo identification or is unable to provide a valid photo identification at the beginning of the virtual visit, the visit may be rescheduled, or the subject may be considered a screen failure.

### **5.4.2 Baseline Assessments**

#### **5.4.2.1 Baseline WURSS-21**

After photo ID verification, the study team will trigger the Baseline WURSS-21 (in appendix section 14.3) for subject self-completion. The purpose of this assessment is to ensure potential participants meet the Inclusion criteria related to the WURSS-21 Symptom domain [minimum score of 5 (moderate) for cough associated with common cold symptoms and at least one other symptom of common cold (at least mild score of 3)]. The study team will review responses as related to determining subject eligibility.

This administration of the WURSS-21 at the Virtual Visit also develops the Baseline for eligible subjects.

#### **5.4.2.2 Baseline Specific Quality of Life Questions**

If the potential participant meets the Inclusion Criteria related to the WURSS-21 Symptom domain, the Baseline for Specific Quality of Life Questions (in appendix section [14.4](#)) will be triggered for subject self-completion.

This administration of the Specific QoL Questions at the Virtual Visit also develops the Baseline for eligible subjects.

### **5.4.3 Eligibility Review**

#### **5.4.3.1 Inclusion/Exclusion Criteria**

Inclusion and exclusion criteria as per Section [4.3](#) and [4.4](#) will be collected via pre-screening and screening surveys and confirmed during the virtual visit with a trained & delegated study team member.

#### **5.4.3.2 Medical History & Prior Medications**

A trained member of the study team will review the subject's medical history and prior medications to confirm subject eligibility to participate in the study.

Relevant medical and surgical history, including allergies or drug sensitivity can be documented by the investigator or designee in the medical history form.

Please refer to section [9](#) for further details on Adverse Event and Serious Adverse Event Monitoring.

#### 5.4.4 Enrolled Subjects and Screen Failures

An enrolled subject is one who has agreed to participate in the clinical study following completion of the eICF and who has directly and successfully met eligibility criteria to proceed beyond the screening visit.

Screen failures are defined as subjects who consent to participate in the clinical study but do not meet study inclusion criteria.

To ensure transparent reporting of screen failure subjects, a minimal set of screen failure information will include demography and screen failure details (e.g., withdrawal of consent, eligibility criteria, any protocol deviations and any adverse events).

Individuals who do not meet the criteria for participation in this study (screen failure) will not be re-screened.

